4.2. Secondary endpoint

- To compare the effect of virtual reality rehabilitation for sensorimotor and proprioceptive deficits in the upper limb to conventional rehabilitation, a comparison is conducted between the assessments at T0 and T1 within the virtual reality treatment group (VR) and the group undergoing rehabilitation as per standard clinical practice (C).
- To assess patient satisfaction with the proposed experimental treatment, a validated questionnaire
 is administered to investigate patient satisfaction. The data are processed by calculating the mean,
 median, mode, and standard deviation for all 8 items. This approach allows for identifying the
 patient's overall considerations regarding the proposed treatment through a statistical summary
 that includes measures of central tendency (mean, median, mode) and data dispersion (standard
 deviation).

5. Data analysis

5.1. Sample size

This study plans to enroll 20 patients, with 10 in the experimental group (VR) and 10 in the control group (C). Given that the study duration is 24 months, with the last 6 months dedicated to statistical analysis, results analysis, and scientific dissemination, the active recruitment and patient inclusion period is estimated to be 18 months. Each patient will participate in the study for 6 weeks (1 week for the baseline assessment at T0, 4 weeks for rehabilitation, and 1 week for the post-treatment assessment at T1). It is believed that the overall number of 20 included patients is achievable within the study's timeframe.

As this is a pilot study, the sample size is considered sufficient to achieve the set objectives, taking into account a potential dropout rate of 20%.

5.2. Statistical analysis

The data analysis will be conducted using the Statistical Package for Social Science (SPSS version 26.0).

The preliminary data obtained from the pilot study will allow for estimating the variation in outcome measures between pre-test and post-test and between the treatment and control groups, providing insights for a potential subsequent trial with a larger sample.

The data will be analyzed based on the stated objectives, which include:

- Descriptive analysis of socio-demographic data for the experimental and control groups, including mean and standard deviation.
- The effect of the virtual reality rehabilitation protocol in the treated group will be assessed by comparing the scores of evaluation scales at pre-test and post-test. Data distribution will be tested using the Shapiro-Wilk test. The non-parametric Friedman test will be used in case of non-normal distribution, while ANOVA will be utilized in case of normal distribution. The significance level will be defined at $p \le 0.05$.
- The effect of the virtual reality rehabilitation protocol compared to the standard rehabilitation protocol will be assessed by comparing the scores of scales at T0 and T1 between the VR and C groups using the non-parametric Mann-Whitney test for independent samples.

6. Relevance

If the experimental hypotheses will be confirmed, the use of the virtual reality rehabilitation system could be implemented in routine clinical practice to rehabilitate sensorimotor integration in patients with stroke outcomes. An innovative approach employing virtual reality techniques aims not only to enhance patient treatment adherence but also to support proprioceptive and sensorimotor rehabilitation through the body illusion paradigm, which is not achievable in traditional rehabilitation. The enhancement of proprioceptive and sensorimotor aspects is considered crucial for the rehabilitation of neuromotor impairment. Therefore, by promptly implementing this type of intervention following a cerebrovascular event, one could hope for a faster and more effective functional recovery.

7. Feasibility

• The Rehabilitation Medicine and Neuro-rehabilitation Unit of the IRCCS Institute of Neurological Sciences in Bologna coordinates both the acute rehabilitation phase (with daily consultations at the Stroke Unit) and the sub-acute phase of the Stroke Clinical Pathway. Consequently, they daily admit patients with stroke outcomes at various stages of the

rehabilitation process. These patients may possess the characteristics to be included in the project.

- The Rehabilitation Medicine and Neuro-rehabilitation Unit of the IRCCS Institute of Neurological Sciences in Bologna is equipped with the VRRS KHYMEIA rehabilitation system.
- The Department of Psychology at the University of Bologna has the expertise to assess the neurocognitive aspects of enrolled patients and administer relevant evaluation scales.
- The Department of Biomedical and Neuromotor Sciences at the University of Bologna has the expertise to assess the neuromotor and proprioceptive aspects of enrolled patients.

8. Ethical aspects

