3.3.4. Post-Treatment Assessment

- a) Motricity Index Test (Bohannon, 1999)
- b) Fugl-Meyer Test (Fugl-Meyer et al., 1975)
- c) Box and Block Test (Mathiowetz et al., 1985)
- d) Functional Indipendence Measure (FIM) (Beninato et al., 2006)
- e) Multidimensional Assessment of Interoceptive Awareness (MAIA) (Machorrinho et al., 2019)

- f) Thumb Location Test (Rand, 2018) NO
- g) Rubber Hand Illusion test (Romano et al., 2021)
- h) STIMA test (Tessari et al., 2015) NO
- i) Attention: trial making test, matrici attentive, fluenza alternata.
- j) Client Satisfaction Questionnaire-8

4. Outcome

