4.1. Primary endpoint

In order to assess the effect that the proposed treatment has on the sensorimotor and proprioceptive impairment of the upper limb, a comparison is conducted between the baseline assessments (T0) and those performed at the end of the 4-week rehabilitation treatment (T1).

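### Section 4.1 names no primary measure and section 5.2 tests unnamed scales at 0.05, so a positive primary result is undefined and could be chosen after the data are seen

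*Protocol*

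**What the plan says.** Section 4.1 (Primary endpoint) sets out to assess "the effect that the proposed treatment has on the sensorimotor and proprioceptive impairment of the upper limb". For this, "a comparison is conducted between the baseline assessments (T0) and those performed at the end" of the four-week treatment. That gives a domain and two time points, but no instrument.

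Section 5.2 (Statistical analysis) assesses the VR arm by "comparing the scores of evaluation scales at pre-test and post-test". The scales are plural and unnamed. On the test it says: "The non-parametric Friedman test will be used in case of non-normal distribution, while ANOVA will be utilized in case of normal distribution". The bullet ends "The significance level will be defined at" p ≤ 0.05. A separate bullet compares scale scores between the VR and control arms by Mann-Whitney, again naming no measure and repeating no threshold.

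Sections 3.3.3 and 3.3.4 list the instruments. Six non-cognitive scales appear at both visits without a NO mark: Motricity Index, Fugl-Meyer, Box and Block, FIM, MAIA and Rubber Hand Illusion. So does an attention set of three tests: "Attention: trial making test, matrici attentive, fluenza alternata". The Thumb Location Test and STIMA are marked NO at the post-treatment visit.

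Sections 5.1 and 5.2 describe a pilot whose data should inform a possible larger trial. Section 6 nevertheless opens "If the experimental hypotheses will be confirmed" and goes on to possible use in routine practice.

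**The concern.** A primary endpoint needs a variable. Section 4.1 supplies a comparison over time and leaves the variable open, so several scales can each be tested at 0.05 and any favourable one presented as the primary result. No order of importance, co-primary requirement or success rule prevents this.

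Two things are at stake. The false-positive rate for the primary question is above the stated 5%. In addition, a reader of the final report could not tell whether the highlighted scale was chosen in advance. Section 6 speaks of the hypotheses being confirmed, but nothing in the protocol says which result would confirm them.

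**Working it through.** The protocol states no family-wise error rate, so there is no figure of its own to reproduce.

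**Step 1. How many scales could be primary?**
- Narrow reading: only scales that plainly measure upper-limb sensorimotor or proprioceptive function and are kept at both visits. By my reading these are Motricity Index, Fugl-Meyer and Box and Block, with Rubber Hand Illusion as a possible fourth: k = 3 or 4.
- Broad reading: every score scheduled at both visits and not marked NO: 6 scales + 3 attention tests, k = 9, before any subscales.

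The text does not say which reading applies.

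**Step 2. Independent tests, each at 0.05, no true T0–T1 change.** The chance of at least one significant result is 1 − 0.95^k:
- k = 3: 1 − 0.95³ = 14.3%
- k = 4: 1 − 0.95⁴ = 18.5%
- k = 9: 1 − 0.95⁹ = 37.0%

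**Step 3. Correlated scales.** Scores from the same patients will be correlated. The protocol gives no correlations, so 0.5 between all pairs is an assumption. I simulated two-sided paired t-tests with n = 10 (the planned VR arm) and n = 8 (10 × 0.8, after the 20% dropout in section 5.1):
- k = 3: about 13%
- k = 4: about 16%
- k = 9: 28 to 29%

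At an assumed correlation of 0.7, k = 9 gives about 22%.

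**Step 4. Does each test really run at 5%?** Steps 2 and 3 take the nominal level. If Friedman were used throughout, it would reduce with two time points to a sign test, whose attained level moves in steps. For 9 independent scales:
- n = 10: attained level 0.0215, so 1 − (1 − 0.0215)⁹ = 17.8%.
- n = 8, asymptotic p-value: attained level 0.0703, so 1 − (1 − 0.0703)⁹ = 48.1%.
- n = 8, exact p-value: attained level 0.0078, so 1 − (1 − 0.0078)⁹ = 6.8%.

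The size therefore also depends on the test that Shapiro-Wilk selects and on the p-value method. The nominal-level range is the fair summary of a plan that sets 0.05.

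**Step 5. After the fix.** With one named measure and one comparison, the nominal error returns to 5%.

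**The case against.** *The domain limits the endpoint.* This stands. A reader might infer that every scale in the battery is primary, but section 4.1 restricts the endpoint to upper-limb sensorimotor and proprioceptive impairment. The attention tests fall outside that, and FIM and MAIA arguably do too. Several baseline tests (Raven, memory, VOSP) are not repeated. The defect is that the set is undefined, not that it is everything.

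*A false positive is not likely.* This also stands for the primary family: both ends of the 14 to 37% range lie below one half. A reader might reach about 60% by adding nine between-arm tests (1 − 0.95¹⁸ = 60.3%). That sum merges the primary and secondary families. It also assumes independence although both use the same VR patients' T1 scores; a correlation of 0.5 across all 18 tests gives about 40%. And section 5.2 states the 0.05 level only in the within-VR bullet.

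*It is a pilot.* This stands in part. Estimating variation for a larger trial is a legitimate aim, and the phrase in section 6 is conditional and not a decision rule. But the protocol still sets a significance threshold, and section 1.1 states hypotheses of effectiveness and of possible superiority to standard rehabilitation.

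*All data will be published.* Section 9 commits to publication whatever the results. That limits selective reporting, but it does not stop one scale being labelled primary afterwards.

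*It belongs in the SAP.* The details of a multiplicity procedure may well be there, and their absence here is not counted. Naming the primary measure belongs under the protocol's own heading of that name.

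**Conclusion.** The point holds as a defect of definition. The protocol names no primary measure, no set of primary scales and no rule for a positive result, while testing plural unnamed scales at 0.05.

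For the within-VR family the chance of at least one false positive is roughly 14 to 37% if the tests are independent, and about 13 to 29% at a correlation of 0.5, against a nominal 5%. These figures rest on 3 to 9 scores, two-sided tests (the protocol does not state sidedness), each attaining its nominal level, and an assumed common correlation. The documents do not support saying that all scales are primary or that a false positive is more likely than not. The change should be made, but given the pilot purpose it does not undermine the study.

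**What to change.** In section 4.1, name one measure already collected at T0 and T1, for example the Fugl-Meyer upper-limb score. State that the upper-limb section is meant, since the assessment lists give only the test's name. Define the variable as the T0–T1 change, and say whether the single 0.05 test is applied within the VR arm (the present primary comparison) or between arms (at present secondary). If the between-arm comparison is chosen, the order of objectives in sections 1.2, 2.1, 2.2 and 4.2 must follow.

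In section 5.2, state that this is the only result carrying the 0.05 test. Report all other scales as secondary or exploratory, with estimates and 95% confidence intervals and no confirmatory claim, or Holm-adjusted if claims are wanted. This includes any proprioceptive measure: a single motor score does not cover proprioception, and the text should say so. In section 6, tie confirmation of the hypotheses to the named result.

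The cost is a few sentences, with no extra patients, visits or assessments. The downside is that the other scales can no longer be claimed as confirmatory.

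### For the non-normal case, the within-arm T0–T1 comparison uses the Friedman test, which with two occasions is only a sign test; a signed-rank test should replace it

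*Protocol*

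**What the plan says.** Protocol section 4.1 defines the primary endpoint by two assessments: "a comparison is conducted between the baseline assessments (T0) and those performed at the end of the 4-week rehabilitation treatment (T1"). Section 5.2 turns this into a within-arm comparison of two occasions: "The effect of the virtual reality rehabilitation protocol in the treated group will be assessed by comparing the scores of evaluation scales at pre-test and" (the sentence closes with the second occasion, T1). The test is then chosen from the data. First, "Data distribution will be tested using the Shapiro-Wilk test"; then, "The non-parametric Friedman test will be used in case of non-normal distribution, while ANOVA will be utilized in case of normal distribution". The significance level is p ≤ 0.05 and the software is SPSS 26.0.

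Section 5.1 plans 10 patients per arm, "taking into account a potential dropout rate of 20"%. The protocol gives no effect size, standard deviation or power. It does not say whether p-values are asymptotic or exact, or whether normality is checked on the scores or on the differences.

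**The concern.** The Friedman test is built for three or more related measurements. Here there are two, and in that case it keeps only the sign of each patient's change. In an arm of 8 to 10 patients, the size of the changes is most of the information there is. A test based on so few signs also has a coarse set of attainable levels, so its real error rate can sit well away from the stated 5% and moves with the number of patients who contribute.

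This affects the analysis attached to the primary objective. It also sits badly with the purpose given in section 5.2, which is to estimate the variation in the outcome measures for a possible larger trial: a sign count gives no estimate of change.

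**Working it through.** **Inputs.** Two occasions (sections 4.1 and 5.2). VR arm n = 10 (5.1). With 20% dropout, 10 × 0.8 = 8 completers if losses are equal in both arms (assumption). Level 0.05 (5.2). Effect sizes and shapes of the changes are assumptions, because the protocol gives none; dz is the mean change divided by the SD of the changes. The plan has no power figure to reproduce.

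**Step 1: Friedman with two occasions.** Let n+ patients rise and n− fall, with no ties. The rank sums are R(T1) = 2n+ + n− and R(T0) = n+ + 2n−. The statistic is [12/(n·2·3)]·(R(T0)² + R(T1)²) − 9n, which reduces to (n+ − n−)²/n on 1 degree of freedom. That is the sign test without continuity correction. Check with n = 10 and 8 rising: rank sums 18 and 12; (2/10)(324 + 144) − 90 = 3.6; and (8 − 2)²/10 = 3.6.

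**Step 2: true level of Friedman taken alone** (asymptotic p; reject above 3.84).
- n = 10: 8 of 10 gives 3.6 (p = 0.058), 9 of 10 gives 6.4 (p = 0.011). Level = 2(1 + 10)/1024 = 2.15%.
- n = 9: 8 of 9 gives 49/9 = 5.44. Level = 2(1 + 9)/512 = 3.9%.
- n = 8: 7 of 8 gives 36/8 = 4.5 (p = 0.034). Level = 2(1 + 8)/256 = 7.03%.
- n = 8 with the exact p: 7 of 8 gives p = 0.070, so all 8 must move the same way. Level = 2/256 = 0.78%.

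Under the standard tie correction, patients with zero change leave the statistic. Ten completers with two unchanged scores on a scale therefore behave like n = 8.

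Exact Wilcoxon signed-rank, for comparison: 4.8% at n = 10 and 3.9% at n = 8.

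**Step 3: power of Friedman alone against exact Wilcoxon** (n = 10, normal changes, 100,000 simulated samples per setting).

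| dz | Friedman | Wilcoxon | relative loss |
|---|---|---|---|
| 0.5 | 13.6% | 28.4% | 52% |
| 0.8 | 34.3% | 60.0% | 43% |
| 1.0 | 51.5% | 78.5% | 34% |
| 1.2 | 67.6% | 90.6% | 25% |

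For t3 changes at dz = 0.5, 0.8 and 1.0 the relative loss is 34%, 18% and 10%.

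**Step 4: the whole rule as written** (n = 10, dz = 0.8). Assumptions: Shapiro-Wilk on the differences, repeated-measures ANOVA (equal to the paired t-test with two occasions), asymptotic Friedman.

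| Shape of changes | Whole rule | Exact Wilcoxon | Rule minus Wilcoxon |
|---|---|---|---|
| Normal | 62% | 60% | +2 points |
| t3 | 78% | 76% | +2 points |
| Lognormal (log-SD 0.6) | 75% | 83% | −8 points |
| Exponential | 70% | 84% | −14 points |

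A separate run of 20,000 samples gave losses of 82.1 − 74.5 = 7.6 and 82.9 − 69.6 = 13.3 points for the two skewed shapes. It put the rule's size under a normal null at 5.1% (n = 10) and 5.3% (n = 8).

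**Step 5: only the samples that Shapiro-Wilk rejects** (n = 10, dz = 0.8). For the lognormal changes, Friedman has 47% power against 77% for Wilcoxon. For t3 changes Friedman is ahead, 67% against 58%. With 8 to 10 patients Shapiro-Wilk rejects in only 23–32% of lognormal and 35–46% of exponential samples, so which test a scale receives is largely chance.

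**The case against.** The strongest reply is that Friedman is not the default. Normal-looking data go to ANOVA, and Shapiro-Wilk at this sample size mostly does not reject, so the figures for Friedman alone describe a branch and not the analysis. This stands, and it is why Step 4 carries the conclusion.

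Three stronger readings are tempting, and the protocol supports none of them.
- A reader might infer that the primary analysis loses about half its power. Even for Friedman alone, that fits only small to moderate effects with normal changes (43–52%) or short-tailed changes. Normal changes pass Shapiro-Wilk about 95% of the time and go to ANOVA. At n = 8 with the asymptotic p, Friedman is not weaker than exact Wilcoxon for normal changes at dz = 0.8 (47% against 43%), partly because its level is higher.
- A reader might infer that the analysis breaches 5%. The 7.0% needs the asymptotic p-value and 8 informative changes. Section 5.1 does not give dropout by arm, and section 5.2 does not name the type of p-value. With the exact p the level is 0.8%, and the whole rule stays near 5% under a normal null.
- A reader might infer that an unqualified ANOVA ignores the pairing. Named beside a related-samples test for a pre/post comparison in one group, repeated measures is the natural reading. What is missing is a label.

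It is also fair that Friedman with two occasions is a valid paired test, inefficient rather than invalid, and that this is a pilot. But the pilot still sets a significance level and wants estimates of change, so the choice of test and summary still matters.

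**Conclusion.** The point holds in a limited form. Section 5.2 names, for the non-normal branch of a two-occasion comparison, a test that is the sign test. This needs no assumption beyond the two time points. Taken alone, its level is 2.2% at n = 10. At n = 8 it is either 7.0% or 0.8%, depending on a p-value method that the protocol does not state.

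The practical cost to the whole rule is moderate and depends on the shape of the changes: about 8 to 14 percentage points of power for skewed changes at n = 10 and dz = 0.8, and essentially none for normal or heavy-tailed ones. Those figures rest on assumed effect sizes and shapes, a normality check on the differences, and a repeated-measures ANOVA. For skewed changes the tests also target slightly different quantities (median, pseudo-median, mean), so the comparison shows the chance of declaring a change and is not a pure efficiency ratio.

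**What to change.** In section 5.2, replace the Shapiro-Wilk switch, the Friedman test and the ANOVA for this comparison with one pre-stated analysis for every scale: the exact Wilcoxon signed-rank test on the T0–T1 differences, reported with the Hodges-Lehmann change and its 95% confidence interval. State that p-values are exact (the asymptotic Wilcoxon p has a level of 5.5% at n = 8) and how zero changes are handled.

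The cost is one sentence in the protocol and no change to data collection. The statistical price is a small loss against the paired t-test if changes are exactly normal: at n = 10 and dz = 0.8, 60% against 62%.

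### The VR-versus-control comparison does not use each patient's own baseline, so it loses precision and does not estimate the between-arm difference in recovery

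*Protocol*

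**What the plan says.** Section 5.2 fixes the between-arm analysis: the effect of VR relative to standard rehabilitation "will be assessed by comparing the scores of scales at T0 and T1 between the VR and C groups using the non-parametric Mann-Whitney test". It names no change score, baseline covariate or group-by-time term.

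Section 4.2 words the same secondary endpoint differently: "a comparison is conducted between the assessments at T0 and T1 within the virtual reality treatment group (VR) and the group undergoing rehabilitation" as in standard practice.

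The question to be answered is set in section 1.2, where the outcome compared between arms is defined as recovery of sensorimotor and proprioceptive function, and section 2.2 repeats it. Section 5.2 adds that the pilot data "will allow for estimating the variation in outcome measures between pre-test and post-test and between the treatment and control groups", with a larger trial in view.

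Sections 3.3.3 and 3.3.4 collect the Motricity Index, Fugl-Meyer, Box and Block, FIM, MAIA, Rubber Hand Illusion and attention tests at both T0 and T1. Section 5.1 plans 10 patients per arm and allows for 20% dropout.

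**The concern.** Recovery is a patient's T1 status relative to that patient's own T0 status. The planned tests do not measure it. At T0 no treatment has been given, so a test between randomised arms can only detect chance imbalance. At T1 the test leaves all between-patient differences in starting severity in the error term. Neither test yields an estimate of the difference in recovery, or an interval for it, although the pilot is meant to inform a later trial.

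This is more than a detail left open for an SAP, because the protocol names both the test and the scores it is applied to. At stake is the trial's only randomised efficacy contrast, with about 8 to 10 patients per arm and baseline scores that are already being collected.

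**Working it through.** **Inputs from the protocol.** 20 patients, 10 per arm (section 5.1). With 20% dropout, 20 × 0.80 = 16 completers, or 8 per arm. The significance level of 0.05 is stated for the within-group analysis in section 5.2 and is taken here as two-sided for the between-group test as well.

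**Inputs not given, hence assumed.** The T0–T1 correlation r is shown from 0.3 to 0.9. SD is set to 1 at both times. A true difference of 0.8 SD is used for illustration. The protocol states no effect size, SD or power, so it has no power figure to reproduce.

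**Step 1: variance relative to a comparison of T1 scores alone.**
- Baseline-adjusted (ANCOVA): 1 − r²
- Change score: 2(1 − r)
- Estimating the slope multiplies the ANCOVA variance by about 1 + 1/(N − 4). This is 1.0625 for N = 20 and 1.083 for N = 16.

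| r | ANCOVA, 1 − r² | with slope cost, N = 20 | with slope cost, N = 16 | Change, 2(1 − r) |
|---|---|---|---|---|
| 0.3 | 0.91 | 0.97 | 0.99 | 1.40 |
| 0.5 | 0.75 | 0.80 | 0.81 | 1.00 |
| 0.7 | 0.51 | 0.54 | 0.55 | 0.60 |
| 0.8 | 0.36 | 0.38 | 0.39 | 0.40 |
| 0.9 | 0.19 | 0.20 | 0.21 | 0.20 |

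Before the slope cost, the share of variance removed is r²: 9%, 25%, 49%, 64% and 81%. It exceeds one half only if r is above √0.5 ≈ 0.71. A change score gains nothing at r = 0.5 and is worse below it.

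**Step 2: difference detectable with 80% power (normal approximation).** For T1 alone this is (1.96 + 0.84) × √(2/n): 1.25 SD at n = 10 per arm and 1.40 SD at n = 8. Multiplying by √(1 − r²) gives the ANCOVA figures for r = 0.5, 0.7 and 0.8: 1.09, 0.89 and 0.75 SD at n = 10, and 1.21, 1.00 and 0.84 SD at n = 8.

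**Step 3: simulated power at 0.8 SD.** Bivariate normal data, exact Mann-Whitney, 6,000 runs per cell.

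| n per arm | r | Mann-Whitney on T1 | Mann-Whitney on change | ANCOVA |
|---|---|---|---|---|
| 10 | 0.5 | 0.36 | 0.36 | 0.48 |
| 10 | 0.7 | 0.35 | 0.54 | 0.64 |
| 10 | 0.8 | 0.35 | 0.72 | 0.78 |
| 8 | 0.5 | 0.32 | 0.32 | 0.39 |
| 8 | 0.7 | 0.30 | 0.46 | 0.52 |
| 8 | 0.8 | 0.29 | 0.63 | 0.67 |

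With no true effect, every method rejects in about 4% to 6% of runs, so the T1 test keeps its type I error. The T0 test rejects in about 4% to 5% of runs whether or not treatment works, so it carries no information on the effect.

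**Step 4: rank methods compared with each other.** Part of the ANCOVA gain on normal data comes from leaving ranks. With 8 per arm, a 1 SD difference and r = 0.8, power is about 0.45 for Mann-Whitney on T1, 0.74 for Quade's rank ANCOVA and 0.84 for ANCOVA. Most of the gain in that setting therefore comes from using the baseline.

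**The case against.** The best defence is that the wording is loose. Comparing scores at T0 and T1 between arms could be meant as comparing T0-to-T1 change, and the purpose stated in section 5.2, to estimate variation between pre-test and post-test and between groups, leans that way. If change was meant, little power is lost at high r: 0.72 against 0.78 for ANCOVA at r = 0.8 with 10 per arm. But the text does not say so, and the ambiguity itself needs correcting.

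It is also fair that this is a secondary contrast in a self-described pilot ("As this is a pilot study, the sample size is considered sufficient to achieve the set objectives"), that no power claim rests on the test, and that normal data favour linear ANCOVA over what bounded or ordinal scales would give.

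A reader might infer three stronger criticisms, which the protocol does not support:
- *Most of the precision is thrown away.* This needs r above about 0.71, and the protocol gives no correlation. Section 3.2 limits severity at both ends (Motricity Index at most 80, with item floors for pinch, elbow and shoulder). Such restriction tends to lower r.
- *The comparison is confounded or biased by baseline imbalance.* Under randomisation, chance imbalance is random error that the test already allows for. It is the same loss of precision seen from another side, not a second harm.
- *Section 4.2 plans to infer superiority from separate within-arm tests.* That is one possible reading of its wording, but its stated purpose is to compare the two treatments, and section 5.2 supplies a between-group test.

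**Conclusion.** The point holds as one of efficiency and target. As written, the between-arm analysis consists of an uninformative test at T0 and a valid but imprecise test at T1, and neither estimates the difference in recovery that sections 1.2 and 2.2 ask for. The size rests on an assumed r. Adjustment saves about 25%, 49% or 64% of the variance at r = 0.5, 0.7 or 0.8 (about 20%, 46% or 62% after the slope cost with 20 patients), and very little at r = 0.3. The power figures further assume normal scores and a 0.8 SD difference, and are illustrative. The change should be made before data are seen because it costs almost nothing. Leaving it out would not make the trial's conclusions invalid.

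**What to change.** In section 5.2, for each scale measured at both T0 and T1, replace the two Mann-Whitney tests with an ANCOVA of the T1 score on arm with the T0 score as covariate. Report the adjusted VR minus control difference with its 95% CI. Name Quade's rank ANCOVA as the distribution-free check. Mann-Whitney on change should not lead, since it gains nothing at r of 0.5 or below. Drop the T0 significance test and describe baseline scores by arm instead.

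Reword section 4.2 to state this same between-arm contrast. Instruments given only at T0, and the two marked NO in the post-treatment list (Thumb Location Test and STIMA), fall outside this analysis as the assessment lists stand.

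The cost is one degree of freedom and a sentence in each section, with no extra patients or visits. ANCOVA is available in SPSS, the package already named.
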